#### 3.3.2 Secondary data analyses

The analysis plan for H2-H9 is as follows:

Summary statistics will be presented by treatment group. Differences between study groups at  $t_1$  will be assessed through  $\chi^2$  or Fisher's exact tests as appropriate. Cohen's d will be calculated as measure for effect size.

The analysis plan for H10 is as follows:

Full scale and subscales will be scored as instructed in the [Decisional Conflict Scale](#) manual. Summary statistics will be presented by treatment group for the full scale and by subscale. To assess differences in scale score distribution between groups, we will perform t-tests or sign tests as appropriate. In case of high positive skew (as common in the literature) we will create binary variables demarcating no conflict versus any conflict and perform  $\chi^2$  tests. Cohen's d will be calculated as measure for effect size.

The analysis plan for H11-H13 is as follows:

Summary statistics will be presented by treatment group. Differences between study groups at  $t_2$  will be assessed through  $\chi^2$  or Fisher's exact tests as appropriate. Cohen's d will be calculated as measure for effect size.

The analysis plan for H14-H18 is as follows:

Summary statistics will be presented for the intervention group.

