##### 2.1.2.2 Secondary variables

- **Number of Patients Reporting PrEP use:** Participants will be contacted at follow-up and asked if took PrEP in the past 3 months regardless of where it was obtained.

- **Patient-Perceived HIV risk:** Participants will be asked about how worried they are about getting HIV in the next 6 months.
- **Knowledge of PrEP:** Participants will be asked a series of questions about PrEP to assess PrEP knowledge.
- **Decisional Conflict:** Participants will be asked questions derived from the Decisional Conflict Scale to provide a measure of decision quality about their HIV prevention decision immediately following their visit.
- **Interpersonal Quality of HIV Prevention Care:** A scale for patient-centered HIV prevention counseling focusing on patient preferences and reflecting satisfaction and confidence in the counseling session, derived from the Interpersonal Quality of Family Planning Care Scale developed by the PI.
- **Intention to Use Any HIV Prevention Method:** Participants will be asked if they plan to use any HIV prevention method after the initial visit.
- **Satisfaction with Information Received about HIV Prevention:** Participants will be asked about their satisfaction with HIV prevention counseling.
- Confidence in decision to use an HIV prevention method. A one-time, one-item measure of certainty of plan to use HIV prevention after the initial visit. Participants can select from 4 options: 1 ("completely unsure"), 2 ("mostly unsure"), 3 ("mostly sure, but not 100%"), or 4 ("100% sure").
- **Perceived Quality of Information Received about HIV Prevention:** Participants will also be asked questions about the perceived quality of the HIV prevention information they received during their health care visit.
- **Acceptability of HIV Prevention Methods:** Participants will be asked to rate their preference for a method (even if they never used it). Participants can select from condoms, PrEP, PEP, treatment as prevention, regular partner testing, or other method.
- **Acceptability of the Decision Support Tool:** Participants in the experimental arm are asked four questions about their experiences using the DST.
- Perception of the Decision Support Tool: Participants in the experimental arm will be asked about the degree to which they liked/disliked the tool. Response options vary: "I did not like it at all", "I somewhat disliked it", "I somewhat liked it", "I really liked it".

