## 2.2 Hypotheses

1. The intervention will result in significantly higher number of PrEP prescriptions compared to the control group.
2. The intervention will result in significantly higher number of individuals reporting PrEP initiation compared to the control group.
3. The intervention will result in significantly higher level of patient-perceived HIV risk post-visit compared to the control group.
4. The intervention group will report significantly higher PrEP knowledge compared to the control group.
5. The intervention group will report significantly higher quality of HIV care compared to the control group.
6. The intervention group will report significantly higher intention to initiate any HIV prevention method compared to the control group.
7. The intervention group will report significantly higher satisfaction with information received about HIV prevention compared to the control group.
8. The intervention group will report significantly higher confidence in decision to use an HIV prevention method compared to the control group.
9. The intervention group will report significantly higher acceptability of HIV prevention methods compared to the control group.
10. The intervention group will report significantly lower decisional conflict, as documented by the full scale and subscales, compared to the control group.
11. The intervention will result in significantly higher number of individuals reporting ongoing PrEP use at 3 months post-visit compared to the control group.
12. A significantly higher proportion of the intervention group will report use of any HIV prevention method at 3 months-post study initiation compared to the control group.
13. A significantly higher proportion of the intervention group will report significantly higher continuation of any HIV prevention method at 3 months-post study initiation compared to the control group.
14. The intervention group will report high acceptability of the DST.
15. A high proportion of the intervention group will report positive impression of the DST.
16. A high proportion of the intervention group will report willingness to use the DST at a future visit.
17. A high proportion of the intervention group will report willingness to recommend to a friend.
18. The intervention group will report high satisfaction with the DST.

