## 1. STATISTICAL METHODOLOGY

### 3.1 General methodology

All outcomes will be presented using descriptive statistics; normally distributed data by the mean and standard deviation (SD) and skewed distributions by the median and interquartile range (IQR). Demography and baseline characteristics will be statistically summarized by treatment group. For binary or categorical items, counts and proportions will be calculated and reported. For continuous outcomes, we will use t-tests for independent samples and for categorical outcome we will employ  $\chi^2$  or Fisher's exact-tests to examine baseline differences between training and control group in demographic data or measured variables. Categorical variables will be assessed and collapsed in cases of small cell sizes for increased power. Scale items of questionnaires (e.g., Decisional Conflict Scale) will be recoded (where applicable) and a scale mean or sum score will be calculated and reported. Composite scale variables will be assessed for skewness through histograms and normal Q-Q plots. Where the normality assumption is not met, median and IQR will be reported. Sign tests will be used to detect differences between groups. Further, in instances where a strong skew is detected, scales will be transformed into binary variables and analyzed as binary data.

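### H8, a four-level ordered item with a directional hypothesis, is assigned a chi-square or Fisher test that ignores the order of the answers

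*SAP*

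**What the plan says.** SAP 2.1.2.2 describes confidence in the decision as "A one-time, one-item measure of certainty of plan to use HIV prevention after the initial visit". It lists four numbered answers that run from complete uncertainty to full certainty. SAP 2.2 words H8 as "The intervention group will report significantly higher confidence in decision to use an HIV prevention method compared to the control group".

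The matching analysis is in SAP 3.3.2, in the block that begins "The analysis plan for H2-H9 is as follows". It provides summary statistics by arm and a comparison at the post-visit survey by chi-square or "Fisher's exact tests as appropriate. Cohen's d will be calculated as measure for effect size". No rank, trend or ordinal test is named for any single item.

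Two provisions of SAP 3.1 come near this. Sign tests are mentioned, but in the sentences about composite scales. There is also a rule that "Categorical variables will be assessed and collapsed in cases of small cell sizes for increased power", which gives no cut point.

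H3 ("The intervention will result in significantly higher level of patient-perceived HIV risk post-visit compared to the control group") and H7 ("The intervention group will report significantly higher satisfaction with information received about HIV prevention compared to the control group") are in the same block. SAP 2.1.2.2 gives neither the number of items nor the response options for them.

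**The concern.** H8 claims movement in one direction along an ordered scale. Pearson's chi-square on a 2×4 table, and Fisher's exact test on the same table, ask only whether the two distributions differ in any way. This has two consequences. A significant p-value can come from a change in spread with no rise in confidence. A genuine rise is tested on 3 degrees of freedom where 1 would do, which usually costs power.

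The planned effect measure does not match the test either. Cohen's d describes a difference in means, while the p-value refers to any difference in shape, so the two can disagree.

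What is at stake is a secondary claim under Aim 1c (decisional certainty), for which H8 is a direct measure.

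**Working it through.** **Inputs from the documents.** H8 has four ordered levels (SAP 2.1.2.2). The level is 0.05 (SAP 3.3), two-sided in SAP 1.5. Planned enrolment is 192 per arm (SAP 1.2), and the sample size calculation uses 320, or 160 per arm (SAP 1.5). That 320 is for the primary outcome: 5% against 15% with 80% power gives 141 per arm uncorrected and 160 per arm with continuity correction, so it reproduces. The plan states no power for H8, so there is no H8 figure to reproduce. Because H8 is measured after the visit and not at 3 months, and loss at that point is not stated, 160 and 192 are both shown.

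**Assumptions.** All answer distributions and odds ratios below are assumed.

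**1. Order is ignored.** For a table with rows 40/40/40/40 and 25/35/45/55, chi-square is 6.457 (p = 0.091). Shuffling the four columns leaves both values unchanged.

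**2. Significance without 'higher'.** Take control 25/25/25/25% and intervention 35/15/15/35%.
- Mean score, control: (1 + 2 + 3 + 4)/4 = 2.5.
- Mean score, intervention: 0.35 + 0.30 + 0.45 + 1.40 = 2.5. Cohen's d on the true means is therefore 0.
- Chi-square noncentrality is n × Σ(p0 − p1)²/(p0 + p1) = 160 × (2 × 0.01/0.60 + 2 × 0.01/0.40) = 13.3.
- On 3 df that gives a rejection rate of 88%. Simulation gives about 88% for chi-square and about 5% for Wilcoxon.

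**3. Power for a real upward shift.** Take control 10/20/40/30% and an odds ratio of 1.8.
- Dividing the cumulative odds (0.1/0.9, 0.3/0.7, 0.7/0.3) by 1.8 gives cumulative proportions 0.058, 0.192 and 0.564, so the intervention answers are about 5.8/13.4/37.2/43.5%.
- Noncentrality at 160 per arm is 160 × 0.0500 = 8.0, which gives 65% on 3 df, in line with the simulated 66%.

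Simulated power, chi-square (3 df) against tie-corrected Wilcoxon, with simulation error up to about one point:

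| Per arm | Odds ratio | Chi-square | Wilcoxon | Loss (points) |
|---|---|---|---|---|
| 160 | 1.3 | 16% | 24% | 8 |
| 160 | 1.6 | 45% | 62% | 17 |
| 160 | 1.8 | 66% | 81% | 15 |
| 160 | 2.0 | 81% | 92% | 11 |
| 160 | 2.5 | 97% | 99% | 2 |
| 192 | 1.6 | 54% | 70% | 16 |
| 192 | 1.8 | 74–75% | 88% | 13 |
| 192 | 2.0 | 88% | 96% | 8 |

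As an analytic check, a noncentrality of (1.960 + 0.842)² = 7.85 gives a 1-df test 80% power. The same noncentrality on 3 df gives 64.5%, a loss of 15.5 points.

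**4. A case that goes the other way.** With 10/30/35/25% against 10/30/22/38%, movement is confined to the top two levels. Chi-square then has about 72% power and Wilcoxon about 25%.

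**5. If the item is collapsed to two levels.** The test then has 1 df and shows direction, but the result depends on the cut. In the odds ratio 1.8 example at 160 per arm, power runs from 28% to 71% over the three possible cuts, all below Wilcoxon's 81%.

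**The case against.** The best defence is that chi-square on a four-level item is valid, that the planned summaries by arm and Cohen's d would show the direction, and that H8 is one secondary hypothesis among 18. Aim 1c is also served by H10, the Decisional Conflict Scale, which has its own analysis. All of this stands. It limits the importance of the point but does not supply a test of the stated claim.

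Four stronger readings are tempting, and the documents do not carry them:
- **That the test cannot show 'higher' at all.** The accompanying summaries show direction, and a two-level version would test it. The supportable statement is that the p-value alone does not establish it.
- **That a fixed loss of about 15 points applies.** That figure belongs to four levels, a proportional-odds shift and mid-range power. It shrinks for small and large effects and can reverse, as step 4 shows.
- **That H3 and H7 share the defect.** Questions about degree of worry and satisfaction suggest graded answers, but their format is not stated. If either is yes/no, the point does not apply to it.
- **That H8 will be collapsed after the data are seen.** The collapsing rule in SAP 3.1 directly follows the sentence on baseline comparisons, and its reach is unclear. The 3-df loss and the open cut point are alternatives, not cumulative faults.

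Wilcoxon is not a pure test of the mean either. With 10/20/40/30% against 20/10/28/42% (means 2.90 and 2.92), chi-square rejects about 96% of the time, but Wilcoxon also rejects about 15%. The example in step 2 is cleaner for that reason.

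**Conclusion.** The point holds for H8. A directional hypothesis on a documented four-level ordered item is paired with an order-blind test, and nothing else in the SAP provides an ordered one. If the levels are kept, significance alone does not support 'higher'. For a general upward shift the expected cost at 160 per arm is about 2 to 17 points of power over odds ratios 1.3 to 2.5, largest in the mid-power range; at 192 per arm and an odds ratio of 1.8 it is about 13 points. These sizes rest on assumed distributions and a proportional-odds shift. If the levels are collapsed instead, the cut point is not prespecified. For H3 and H7 the point is conditional on response options that the documents do not give. The primary analysis is untouched.

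**What to change.** In SAP 3.3.2, take H8 out of the common block and prespecify a Wilcoxon rank-sum test or a proportional-odds model. In place of Cohen's d, report the common odds ratio or the probability of a higher answer, with a 95% confidence interval, and show the full answer distribution by arm. State that the levels of H8 will not be collapsed after the data are seen.

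State the number of items and the response options for H3 and H7, and apply the same analysis to each if its answers are ordered with more than two levels.

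The cost is a short SAP edit with no new data. The trade-off is less power to detect differences that are not a general move up or down; the displayed distributions would still let a reader see such a pattern.

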### 3.4 Safety analysis

#### 3.4.1 Analysis of adverse events (AEs)

The number and percentage of subjects who had at least one serious adverse event, classification of serious adverse event, adverse events of special interest and classification of adverse events of special interest from study will be provided.

## 4. DATA PROCESSING CONVENTIONS

### 4.1 Definition of baseline

In this study, baseline values are defined as those data collected before intervention (screening visit).

### 4.2 Missing data

We will report proportions of missing values for all collected variables where needed. Baseline characteristics missing data will be imputed by multiple imputation with chained equations (MICE) procedures as appropriate.

### 4.3 Statistical analysis software

All statistical analysis and summary will be carried out using Stata version 16.1 or higher.
